14.2.1 Serious adverse events

All serious TEAEs will be presented in a summary table by SOC, PT, and maximum CTCAE grade (see paragraph above). In addition to the summary tables, a detailed listing of all SAEs will be provided in CSR Section 14.3.2.

14.2.2 Adverse events leading to withdrawal

All AEs collected with a study medication action taken as “withdrawn” will be presented in a summary table by SOC, PT, and maximum CTCAE grade (see Section 14.2). In addition to the summary tables, a detailed listing of all TEAEs leading to study drug discontinuation will be provided in CSR Section 14.3.2.

14.2.3 Deaths

All patient deaths during this study will be presented in a data listing, which will be provided in CSR Section 14.3.2. Data presented will include date of death, date of last visit, date of 1st dose, days from 1st dose until death, date of last dose, number of days from last dose of study drug to death, number of AEs (if applicable), cause of death, and relationship of cause of death to study drug.

14.2.4 Infusion related reaction symptoms

For the overall summary of AEs as well as the overall summary of IRRs several IRR symptoms reported for one infusion will be grouped into one single IRR and counted as one event.

All individual IRR symptoms will be presented in a summary table by SOC, PT, and maximum CTCAE grade (see paragraph above). Summary tables by SOC, PT, and maximum CTCAE grade will also be provided for all IRR symptoms leading to study and/or treatment withdrawal and all serious IRR symptoms. Also, the frequency of IRR symptoms resolved within 24 hours will be presented.

In addition to the summary tables, a detailed listing of all IRR symptoms will be provided in CSR Section 14.3.2.

14.3 Vital signs

Vital signs (systolic and diastolic blood pressure, heart rate, body temperature, respiratory rate, and oxygen saturation measured with pulse oximetry) are the 1st secondary endpoint related to the primary objective of this study and are measured at the screening visit and at each infusion.

At Weeks 1 to 8, assessments will be performed at pre-infusion, 1 hour (+/- 5 minutes), 2 hours (+/- 5 minutes) and 3 hours (+/- 5 minutes) after start of infusion, within 1 hour after end of infusion, within 6 to 7 hours after start of infusion, within 8 to 12 hours after start of infusion, and on Days 2 and 3. In addition, at Weeks 1 and 2 the assessments are also done on Day 5.

At Weeks 9 to 24, assessments will be performed at pre-infusion, 2 hours (+/- 5 minutes) after start of each infusion and within 1 hour after end of each infusion. At Weeks 12 and 24, the assessments are also done on Day 3.

In case of prolonged SOBI003 infusions (i.e., > 4 hours) and regardless of which Study Week, the assessment schedule should be adjusted so that vital signs are assessed every hour during infusion and within an hour of completion of the infusion. After completed SOBI003 infusion, vital signs are also assessed on Days 2 and 3 (where Day 1 equals the start of the SOBI003 infusion). Depending on the duration of the infusion, the assessment at 8 to 12 hours after start of infusion may also apply. In case of need to prolong infusions (i.e., > 4 hours) at any time during the study, pulse oximetry monitoring will be applied, as judged by the investigator.

Vital signs values will be listed and summarized descriptively by visit and time point including changes from Baseline.

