The results of the above assessments will constitute the patient's baseline.

The patient should not have evidence of ongoing infection, as judged by the investigator. In such case, the 1st infusion should be postponed until the infection has resolved. Antibiotic treatment should also be completed, when applicable, prior to start of SOBI003 treatment.

Within 30 to 60 minutes prior to start of the SOBI003 infusion, a single dose of an oral non-sedative antihistamine is administered. A pulse-oximeter is applied and SOBI003 infusion is initiated. Refer to Section 7.4.6 for infusion details. Day 1 of Week 1 constitutes the day of the first SOBI003 infusion.

Adverse events and concomitant medications are captured continuously from the start of the first infusion until study completion.

At hourly intervals during the infusion, (i.e., at approximately 1, 2 and 3 hours after start of infusion) vital signs, general appearance and skin are assessed.

Upon completion of the 4-hour infusion, and as soon as practically possible, a PK blood sample is obtained. Within an hour of completion of the infusion, vital signs, general appearance and skin are assessed. In addition, a 12-lead ECG is obtained and the continuous pulse oximetry is discontinued.

Vital signs (including oxygen saturation), general appearance and skin are assessed on Day 1 (within 6 to 7 hours after start of infusion, and also within 8 to 12 hours after start of infusion) and on Days 2, 3 and 5.

Blood and urine is collected for safety laboratory analyses on Day 3. Blood is collected for PK analyses at Days 1, 2, 3, 5, and 6 at time points specified in Section 7.5.6.1.

Well in advance of discharge at Week 3, the parents/caregivers will be trained on signs and symptoms of acute and delayed hypersensitivity reactions (both verbally and in writing), and informed on the importance to seek immediate medical attention if hypersensitivity reactions occurs. Acute hypersensitivity reactions include rash, itching, sweating, swelling of lips/tongue/face, vomiting, noisy breathing, dizziness, fainting, and delayed reactions includes dermatological events/skin reactions such as contact dermatitis, maculopapular rash/eruptions,

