4.1 Overall study design and plan

This is an open-label, non-controlled, parallel, sequential ascending multiple-dose, multicenter study to assess the dose related safety, tolerability, pharmacokinetics (PK), and pharmacodynamics (PD) of SOBI003 in pediatric MPS IIIA patients. An overview for the study design is presented in [Figure 1](#).

In February 2020, Sobi decided to discontinue the SOBI003 program. At the time of the decision, 3 patients had been included in Cohort 1 and 3 patients in Cohort 2 of the FIH study (SOBI003-001). All patients had been enrolled in the Extension study (SOBI00-002) and will have the possibility to continue their treatment for a total of two years. Thus, Cohort 3 in the FIH study (SOBI003-001) will not be started. Statistical analysis for the FIH study (SOBI003-001) CSR will be done for Cohort 1 and 2.

Figure 1 Overview for study design for Study SOBI003-001

SOBI003 is administered as weekly intravenous (i.v.) infusions over a period of time of 4 hours. The study treatment period comprises 24 weekly infusions. Prior to initiation of each infusion, the patients are pre-treated with a single dose of non-sedative antihistamine. If infusion-related reactions occur, then the infusion duration may be expanded up to 24 hours and supportive medication may be administered, at the discretion of the investigator.

The study is planned to consist of 3 dose cohorts, each comprising 3 patients, provided that no significant safety concern arise. An additional cohort comprising 3 patients may be added, if deemed necessary to more accurately characterize the safety, tolerability, PK or PD.

The screening visit can be performed up to 12 weeks prior to the first SOBI003 infusion. At the screening visit, the MPS IIIA diagnosis is verified and the genotype is determined at a central laboratory. Patients are assigned to a dose cohort in consecutive order as the eligibility criteria have been confirmed, with prioritization of the younger patients.

Treatment initiations will be staggered within each cohort in order to be able to observe, interpret and treat possible adverse reactions and to ensure that such reactions can be dealt with promptly. For each cohort, safety review committee (SRC) meetings are scheduled approximately 3 weeks after completion of the 3rd patient's 4th dose administration. Based on the safety, immunogenicity, PK and PD data, the SRC will determine what dose to apply in the next cohort.

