8.4.3 Baseline and change from baseline

Baseline is defined as the last available assessment prior to 1st infusion of study treatment.

Change from baseline = (post-baseline value – baseline value).

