14.1 Drug exposure

Upon provision of signed informed consent, patients are assigned a patient number and allocated to a dose cohort in strict consecutive order. Thus, the first 3 enrolled patients are assigned to Cohort 1 and administrations of SOBI003 at 3 mg/kg/week; for Cohorts 2 and 3, dose levels of 10 mg/kg/week and 20 mg/kg/week are planned.

At the time of the 1st SOBI003 infusion, the patient should not have any clinically significant evidence of an ongoing infection, or an ongoing treatment with antibiotics. In such cases, the 1st infusion should be postponed until the infection has resolved.

SOBI003 is administered as weekly i.v. infusions over a period of time of 4 hours. The study treatment period comprises 24 weekly infusions. For each weekly visit, date and time of administration will be recorded in the eCRF, as well as reasons for infusion stop (if any), dose level, SOBI003 volume, total infusion volume administered, and dosing action taken (e.g., “withdrawn”). All data will be listed.

In addition, actual dose received in mg, actual dose level received in mg/kg (see Section 8.4.8), and study treatment exposure in weeks will be calculated (see Section 8.4.2). These data will be listed and summarized.

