An Infusion related reaction (IRR) has been defined as any AE occurring during an infusion or within 24 hours after end of infusion and which is considered related to SOBI003 treatment as judged by the investigator. IRRs may appear as symptoms such as rash, urticaria, erythema, emesis, loose stools, fever, alterations in heart rate, and blood pressure, but could also include other symptoms considered related to the infusion. Such symptoms (by PT and SOC) will be grouped into separate IRRs. There can be one IRR per infusion, in case several IRR symptoms are reported for one infusion they will be counted as one single IRR.

TEAEs will also be classified according to the patients ADA status (positive, negative, boosted, unknown) at the time of the AE occurrence.

All AEs will be summarized by dose cohort. The following analyses will be performed:

- Overall summary of AEs (overall, non-treatment emergent SAEs, TEAEs, drug-related TEAEs, non-serious TEAEs, serious TEAEs, serious drug-related TEAEs, TEAEs leading to study and/or treatment withdrawal, drug-related TEAEs leading to study and/or treatment withdrawal, serious TEAEs leading to study and/or treatment withdrawal, TEAEs leading to death, IRRs)
- Overall summary of IRRs (overall, serious IRRs, IRRs leading to study and/or treatment withdrawal). There can be one IRR per infusion, in case several IRR symptoms are reported for one infusion they will be counted as one single IRR.
- TEAEs by SOC and PT
- TEAEs by SOC and PT and by maximum CTCAE grade
- Drug-related TEAEs by SOC and PT
- Drug-related TEAEs by SOC and PT by maximum CTCAE grade
- Serious TEAEs by SOC and PT
- Serious TEAEs by SOC and PT by maximum CTCAE grade
- Serious drug-related TEAEs by SOC and PT
- Serious drug-related TEAEs by SOC and PT by maximum CTCAE grade
- TEAEs leading to study and/or treatment withdrawal by SOC and PT
- TEAEs leading to study and/or treatment withdrawal by SOC and PT by maximum CTCAE grade

- Drug-related TEAEs leading to study and/or treatment withdrawal by SOC and PT
- Drug-related TEAEs leading to study and/or treatment withdrawal by SOC and PT by maximum CTCAE grade
- TEAEs by SOC and PT and by ADA status
- IRR symptoms by SOC and PT
- IRR symptoms by SOC and PT by maximum CTCAE grade
- Serious IRR symptoms by SOC and PT
- Serious IRR symptoms by SOC and PT by maximum CTCAE grade
- IRR symptoms leading to study and/or treatment withdrawal by SOC and PT

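### From the second infusion on, the only planned vital-sign change score mixes the acute infusion effect with drift since Week 1; a same-visit change should be added

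*SAP*

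**What the plan says.** SAP 14.3 gives the whole analysis of vital signs in one sentence: "Vital signs values will be listed and summarized descriptively by visit and time point including changes from Baseline". SAP 8.4.3 fixes the reference value for every variable: "Baseline is defined as the last available assessment prior to 1st infusion of study treatment". Protocol 7.5.1.4 lists the assessments made before the Week 1 infusion, vital signs among them, and adds: "The results of the above assessments will constitute the patient's baseline". In normal conduct, then, Baseline is the Week 1 pre-infusion reading.

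The measurement schedule is built around each infusion. SAP 14.3 states: "At Weeks 1 to 8, assessments will be performed at pre-infusion, 1 hour (+/- 5 minutes), 2 hours (+/- 5 minutes) and 3 hours", followed by readings within 1 hour of the end, at 6 to 7 hours and at 8 to 12 hours after the start, and on later days. For the rest of the study: "At Weeks 9 to 24, assessments will be performed at pre-infusion, 2 hours (+/- 5 minutes) after start of each infusion", with one more reading within 1 hour of the end. SAP 14.1 gives the number of infusions: "The study treatment period comprises 24 weekly infusions".

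The output index in SAP 19.2 has one vital-signs table (14.3.4.2.1, by visit, time point and change from Baseline) and one figure of individual patient plots (14.3.4.2.2). Listing 16.2.8.2.1 shows every value. Neither document plans a change from the pre-infusion value of the same visit.

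**The concern.** Readings before, during and after an infusion on the same day are useful mainly because they are paired: the child is his or her own control within hours. The planned score does not use that pairing after Week 1. At Week 20, for example, the change at 2 hours is the infusion effect plus whatever has happened to heart rate or blood pressure in a child aged 1 to 6 years since Week 1, plus ordinary day-to-day variation. All of a child's changes also share one reference reading, taken on the first infusion day.

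Vital signs are a secondary endpoint for the primary safety objective. The Protocol expects infusion reactions (5.3) and an immune response to SOBI003 (5.1.4), so later infusions are of real interest, and the planned score isolates the infusion only at the first. There is little averaging to help. SAP 4.1 records that, when the program was discontinued, "3 patients had been included in Cohort 1 and 3 patients in Cohort 2".

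**Working it through.** The plan states no sample size, error rate or precision for vital signs, so there is no figure of the plan's own to reproduce. Two checks apply.

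**1. How many readings are affected.** Inputs are from SAP 14.3 and 14.1, assuming 4-hour infusions and a complete schedule.

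- Weeks 1 to 8: 6 Day 1 readings after infusion start (1 h, 2 h, 3 h, within 1 h of end, 6–7 h, 8–12 h). 8 × 6 = 48.
- Weeks 9 to 24: 2 such readings (2 h, within 1 h of end). 16 × 2 = 32.
- Total per child: 48 + 32 = 80.
- Week 1: its 6 readings are already compared with that day's pre-infusion value, because that value is Baseline.
- Remaining: 80 − 6 = 74, or 74/80 = 92.5%, at 23 of 24 infusions. Each is compared with a value from an earlier week, up to 23 weeks before.

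**2. What the distant reference does to the score.** Write a reading as child level + visit effect (SD sB, between days) + within-day noise (SD sW), plus any drift since Week 1 and, after infusion start, the acute effect. Take the visit effects and the noise terms as independent. From Week 2 on:

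- Variance of change from Baseline = 2sB² + 2sW²; its mean is acute effect + drift.
- Variance of change from the same visit's pre-infusion value = 2sW²; its mean is the acute effect.
- Ratio of SDs = sqrt(1 + sB²/sW²).

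| Assumed sB/sW | SD ratio |
|---|---|
| 0 | 1.00 |
| 0.5 | sqrt(1.25) = 1.12 |
| 1 | sqrt(2) = 1.41 |
| 2 | sqrt(5) = 2.24 |

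An illustration for heart rate with n = 3, in which every input is assumed: acute effect +10 bpm, drift −5 bpm, sW = 6 bpm.

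- Mean change from Baseline = 10 − 5 = 5 bpm. Its SE is sqrt(2(sB² + 36)/3), which is 4.9 for sB = 0, 6.9 for sB = 6 and 11.0 for sB = 12.
- Mean same-visit change = 10 bpm. Its SE is sqrt(2 × 36/3) = 4.9 whatever sB is.

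A simulation of 200,000 runs per setting agreed with these values.

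**3. What the planned table can still give.** For the same children, (mean post − mean Baseline) − (mean pre − mean Baseline) = mean post − mean pre. With complete data the mean acute change is therefore recoverable exactly; the simulation differences were rounding error only. The SD, median and range of the paired change are not recoverable, because they depend on how pre and post values pair within each child. With missing readings even the mean may not be, since the two means can cover different children.

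**The case against.** The case for leaving the plan alone is fairly strong.

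- **Raw values are shown.** SAP 14.3 summarises the values as well as the changes, and pre-infusion is a scheduled time point. Each visit's pre-infusion summary therefore stands in the same table as its later readings. With six children, the listings and individual plots are a practical way to see a consistent shift.
- **Acute reactions have their own analysis.** Protocol 7.5.5.5 sends clinically significant vital signs to adverse-event reporting. SAP 14.2 counts related events during an infusion or within 24 hours after its end as infusion related reactions and names "fever, alterations in heart rate, and blood pressure" among the symptoms. These have their own tables and listing.
- **The size is assumed.** No vital-sign SD appears in either document, and with no between-day variation the SD penalty is nil. No test on vital signs is planned in SAP 14.3.
- **Change from pre-treatment Baseline has a purpose.** From Week 2 the same-day pre-infusion value is itself an on-treatment value, so only the fixed Baseline compares on-infusion readings with the untreated state.

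All of this stands, and it limits the point. A reader might infer that the acute effect is hidden at every infusion. The documents do not support that: Week 1 is already a same-day comparison, and at later weeks the values needed are tabulated, listed and plotted. A reader might also infer that the fixed Baseline is wrong and should be replaced; the last item above answers that.

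The objection does not remove the gap. The adverse-event route requires a judgement of clinical significance, and the infusion-reaction route also requires a judgement of relatedness. A consistent shift below those thresholds shows only in the vital-signs outputs. Those have no out-of-range or shift tables of the kind planned for clinical chemistry, hematology and coagulation.

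**Conclusion.** The point holds in limited form. From the second infusion on, the only planned change score does not isolate the acute effect, although the data to do so are collected at every infusion. The count of 74 of 80 readings follows from the schedule. The SD inflation of 1.00 to 2.24 times rests on assumed ratios sB/sW of 0 to 2 and on the simple variance model above; drift, if present, enters the mean change in full. The practical loss is the spread, median and range of the paired within-visit change, and its mean where readings are missing. The effect on conclusions is modest, because the analysis is descriptive, has three children per cohort and is backed by listings, plots and adverse-event reporting. No planned conclusion becomes wrong. This is an inexpensive improvement to a summary that serves the primary objective.

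**What to change.** In SAP 14.3 and Table 14.3.4.2.1, keep change from Baseline at all time points. Add, for each Day 1 time point during and after infusion, the change from the same visit's pre-infusion value, with n, mean, SD, median, minimum and maximum. At Week 1 the two scores normally coincide, which a footnote can say. Readings on later days can stay with change from Baseline alone.

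The cost is one derived variable and additional rows or columns in an existing table. No new data, visits or procedures are needed, and nothing in patient management changes.

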14.4 Laboratory data

Laboratory safety variables are the 2nd secondary endpoint related to the primary objective of this study. Clinical chemistry, hematology, coagulation and urine analyses are conducted at a central laboratory (BARC). The time points for sample collection are described in [Table 6](#), together with the analyses performed at each sampling occasion.

Table 6 Safety laboratory assessment time points

Analyses	Study visit	Sampling time point(s)
Clinical chemistry (1.5 mL blood): Aspartate aminotransferase (AST), Alanine aminotransferase (ALT), Total bilirubin (if >upper limit of normal [ULN] then also direct and indirect bilirubin), Creatinine, Albumin, Potassium (K), Sodium (Na), Calcium (Ca), non-fasting Glucose, and C-reactive protein (CRP).	Screening	
	Weeks 1 to 3	pre-infusion (Day 1) and Day 3
Hematology (0.5 mL blood): Hemoglobin (Hb), Erythrocytes, White blood cell count (WBC), Differential blood count and Platelet count.	Weeks 4 to 8	pre-infusion
	Weeks 10, 12, 14, 16, 18, 20, and 22	pre-infusion
Coagulation (1.7 mL): PT/INR, APTT, and Fibrinogen. Urinalysis (dip-stick analyses, central laboratory): pH, Glucose, Proteins, and Blood	Week 24	Day 3
	Baseline	
C-reactive protein (CRP), IL-1ra, TNF α , IgE, and tryptase (6.4 mL blood)	In case of infusion/anaphylactic reaction	

Clinical laboratory values will be listed and summarized descriptively by visit and time point including changes from baseline. A separate listing will be provided for abnormal results. Shift tables will be used to evaluate categorical changes from Baseline to End of Study visit by examining the proportion of patients whose test values are outside the normal ranges. Patient plots will illustrate laboratory results for each parameter graphically.

14.5 Immunogenicity

Serum samples are collected at Baseline (same time as the CSF sample is collected) and prior to start of SOBI003 infusion at Weeks 2, 4, 8, 12, 16, 20, and 24, and if applicable at Early Termination of SOBI003 treatment, CSF samples (0.5 mL) are collected at Baseline and at Weeks 12 and 24.

The analysis of immunogenicity will in general be based on the immunogenicity analysis set. In case any patient has missing baseline, all immunogenicity analyses without considering baseline will be performed on a second immunogenicity analysis set including all patients with sufficient blood samples for ADA testing (i.e. including those with missing baseline).

The analyses of PK by ADA status at baseline will be based on the PKAS.

The following definitions will apply as defined in the harmonized terminology for immunogenicity (10):

- **Evaluable patient:** A patients with at least 1 sample taken after study drug administration that is appropriate for ADA testing (with reportable result).
- **ADA-positive sample:** When ADA is detected in a sample, the sample is considered positive.
- **Baseline ADA:** Pre-existing antibodies detected at baseline.
- **Treatment induced ADA:** de novo development following administration of study drug (i.e., formation of ADA any time after the initial study drug administration in a patient without preexisting ADA).
- **Treatment boosted ADA:** Baseline ADA boosted to higher level following study drug administration (i.e., at any time after the initial study drug administration the ADA titer is greater than the baseline titer by a factor of four).
- **ADA-positive patient:** A patient with at least 1 treatment-induced or treatment-boosted ADA-positive sample at any time during the treatment or follow-up observation period.
- **ADA-negative patient:** A patient without a treatment induced or treatment-boosted ADA-positive sample during the treatment or follow-up observation period.
- **Baseline ADA positive patient:** A patient with ADA at baseline. Such patient can have treatment boosted ADA after dosing.

Note that the requirement for inclusion in the immunogenicity set of at least 1 post-dose ADA assessment means that all patients in the immunogenicity set are “evaluable patients”.

The immunogenicity data will be listed for each patient and individual patient plots of titer measurement over time presented. Titer measurements will be summarized by visit using descriptive statistics by dose cohort and overall. Immunogenicity will be evaluated in regards antibody prevalence (pre-existing antibodies), antibody incidence, titer and boosting following dosing, impact on PK and PD responses.

A summary of ADA positive patients over time will be presented. For each visit this will summarize the number of patients who were ADA positive (treatment induced or treatment boosted ADA). A summary of ADA change from baseline immune response will be presented, summarizing the overall ADA incidence (number of ADA positive patients) as well as the numbers of patients for whom this was treatment induced ADA and treatment boosted ADA, together with summaries of titer.

Figures for each patient will be produced with titer and TEAEs plotted against time with ADA status (positive, negative, boosted) will be marked as well.

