7.5.5.3 Immunogenicity

Serum and CSF samples are collected for central laboratory analysis (York Bioanalytical Solutions Limited, [name]) of SOBI003 ADAs by a validated immunoassay method. Assays are being developed for assessment of neutralizing antibodies, both for antibodies inhibiting cellular uptake and for enzyme activity inhibiting antibodies (BioAgilytix, [name]). At each sampling occasion, a blood volume of 1.5 mL will be collected.

Serum samples are collected at Baseline (same time as the CSF sample is collected) and prior to start of SOBI003 infusion at Weeks 2, 4, 8, 12, and 24, and if applicable at Early Termination of SOBI003 treatment. Triplicate aliquots are required for each sampling time point.

CSF samples (0.5 mL) are collected at Baseline and at Weeks 12 and 24.

For patients with an ADA-positive serum sample, the following will also be determined in serum: ADA titer, IgG subclasses, and presence of NAb.

For patients with an ADA-positive CSF sample, the following will also be determined in CSF: ADA titer and presence of NAb.

Should any patient permanently discontinue SOBI003 treatment prior to Week 24, then serum samples for ADA assessments should be obtained as soon as possible after the decision of Early Termination of SOBI003 treatment as well as 30 to 40 days after the last SOBI003 administration. Should the latter sample be ADA-positive, then ADA samplings will continue at approximately monthly basis until the ADA has disappeared or titers have stabilized at a lower level.

The impact of ADAs on the safety, tolerability, and PK of SOBI003 will be explored, as well as the potential impact on HS levels in CSF, serum and urine.

Sampling details are provided separately in the study-specific Laboratory Manual.

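### SAP 14.5 promises to evaluate the impact of antibodies on PK and PD, but the only PK grouping it specifies is ADA status at baseline, which cannot separate seroconverters from non-seroconverters

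*SAP*

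**What the plan says.** - **Aim.** Protocol 7.5.5.3: "The impact of ADAs on the safety, tolerability, and PK of SOBI003 will be explored". The same sentence extends the aim to HS in CSF, serum and urine. SAP 14.5 says immunogenicity will be evaluated for, among other things, "titer and boosting following dosing, impact on PK and PD responses".
- **Specified PK grouping.** SAP 14.5: "The analyses of PK by ADA status at baseline will be based on the PKAS".
- **Baseline.** SAP 8.4.3: "Baseline is defined as the last available assessment prior to 1st infusion of study treatment".
- **ADA categories.** In SAP 14.5, baseline ADA means "Pre-existing antibodies detected at baseline". Treatment-induced ADA means "de novo development following administration of study drug", in a patient who had none beforehand.
- **ADA sampling.** Serum is taken at baseline and "prior to start of SOBI003 infusion at Weeks 2, 4, 8, 12, 16, 20, and 24" (SAP 14.5). Protocol 7.5.6.1 pairs a PK sample with each immunogenicity sample.
- **Safety, for contrast.** SAP 14.2 classifies each TEAE by the patient's ADA status when the event occurred, and the output index gives this its own table (14.3.1.14).

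**The concern.** The question the trial raises is about antibodies that develop on treatment. Protocol 5.1.4 reports that ADAs appeared to affect exposure in cynomolgus monkeys and says an immune reaction may be expected in patients. Protocol 7.4.7 foresees patients whose high titers affect PK/PD. A grouping fixed before the first infusion carries no information on that process.

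If exposure or HS response fell in patients who seroconverted, the specified grouping would average them with patients who did not. Any link would then have to be put together after the data were seen, with the choice of parameters, visits and ADA measure left open.

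**Working it through.** The plan gives no figure to reproduce. The check is mainly a comparison of definitions, followed by one illustration.

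**Step 1. Where each type of patient falls.** Using the SAP 14.5 definitions:

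| Course on treatment | SAP patient-level class | Group in the baseline analysis |
|---|---|---|
| None at baseline, none later | ADA-negative | Baseline-negative |
| None at baseline, induced later | ADA-positive | Baseline-negative |
| Present at baseline, not boosted | ADA-negative | Baseline-positive |
| Present at baseline, boosted | ADA-positive | Baseline-positive |

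Each baseline group can hold both ADA-positive and ADA-negative patients as the SAP itself classes them. All treatment-induced cases are in one group, beside the patients who never seroconvert. This follows from the definitions and needs no assumption about prevalence.

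**Step 2. Whether another specified analysis fills the gap.**
- SAP 15.5.3 groups PK by dose level and demographics. SAP 16.2.3 does so for HS by treatment and demographics.
- The steady-state models (SAP 15.6) contain no ADA term. The dose-proportionality model (SAP 15.7) names only weight or age as possible covariates.
- The individual figures described in SAP 14.5 plot titer with TEAEs, not with exposure or HS.
- The population PK endpoint (SAP 3.4.3) does not name ADA as a covariate.
- The output index (SAP 19.2) lists no PK or HS output by ADA status.
- SAP 17 records that the HS mixed models were dropped. It does not say the ADA-impact aim was dropped.

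**Step 3. Whether time-matched data exist** (SAP 14.5, Table 7 and 16.1).

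| Week | Serum ADA | Serum PK | Serum and urine HS | CSF HS |
|---|---|---|---|---|
| 2, 8, 16, 20 | yes | pre-infusion and end of infusion* | yes | no |
| 4 | yes | profile | yes | no |
| 12, 24 | yes | profile | yes | yes |

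*At Week 2 the lightest weight band has only the pre-infusion sample.

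All seven post-dose ADA visits have PK, serum HS and urine HS. Week 1 also has a PK profile, reduced in lighter patients.

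**Step 4. How thin the baseline comparison might be.** SAP 4.1 gives n = 3 + 3 = 6 patients. The baseline prevalence p is an assumption. The formulas are P(no baseline-positive patient) = (1 − p)^6, and P(at least 2 in each group) = the sum over x = 2, 3, 4 of C(6,x) p^x (1 − p)^(6−x).

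| Assumed p | P(no baseline-positive patient) | P(at least 2 in each group) |
|---|---|---|
| 5% | 0.735 | 0.033 |
| 10% | 0.531 | 0.114 |
| 20% | 0.262 | 0.343 |
| 30% | 0.118 | 0.569 |

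For example, at 10%, 0.9^6 = 0.531.

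**The case against.** **The aim is stated, and the quoted sentence only assigns an analysis set.** Both are true. SAP 14.5 does commit to evaluating impact on PK and PD after dosing, so it would be wrong to say the plan ignores it. But that commitment names no grouping, method, analysis set or output. If the baseline sentence is read as no more than an analysis-set rule, then no PK-by-ADA grouping is specified at all, and the gap remains.

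**Six patients can be read one by one.** This stands in part. A reader might infer that an antibody effect on exposure could not be detected in this trial. The documents do not support that. The SAP plans individual titer plots, individual PK profiles, individual trough and end-of-infusion plots, individual serum and urine HS profiles, and ADA, PK and HS listings. A seroconverter with falling exposure could be noticed by laying these side by side. What is missing is a specified analysis that links them.

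**The index is weak evidence.** This stands. The titer summaries promised in SAP 14.5 are not named in the index, and neither is the baseline PK-by-ADA analysis. Absence from the index does not show that a post-dose analysis was ruled out.

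**The baseline groups need not be empty.** This stands. Exclusion of prior ERT for MPS IIIA makes few positives plausible, but the documents give no prevalence. The point rests on Step 1, not on Step 4.

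**Time-matched groups can also fail.** This stands and shapes the fix. Protocol 5.1.4 calls ADA development common with enzyme replacement, so there may be no ADA-negative group by Week 12 or 24. Splitting two cohorts of three by status, titer and neutralizing antibody (NAb) gives cells of 0 to 3, with status possibly confounded with dose. The protocol describes the NAb assays as still in development.

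**The programme has been discontinued (SAP 4.1) and this aim is exploratory.** That limits the stakes. It does not make the baseline grouping suitable for the question.

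**Conclusion.** The point holds as one about the specified analysis. SAP 14.5 commits to evaluating the impact of ADA on PK and PD, but the one PK grouping it names cannot separate treatment-induced seroconverters from patients who never seroconvert. That conclusion rests only on the SAP's own definitions.

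The further risk of an empty or one-patient group depends on an assumed prevalence. Over 5% to 30%, the chance of no baseline-positive patient among six runs from 0.735 down to 0.118.

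The importance is moderate. The primary endpoint (TEAEs and SAEs) is unaffected, and TEAEs are already handled by ADA status at the time of the event. A stated exploratory aim, however, has no suitable specified analysis, although the data for one are already being collected.

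**What to change.** Replace the baseline grouping in SAP 14.5 with descriptive, time-matched displays:

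1. **Main display: one overlay per patient.** Show ADA status and titer (and NAb where available) over time with AUC0-168h, CL, end-of-infusion and trough concentrations, and change in HS. Use serum and urine HS at the ADA visits and CSF HS at Weeks 12 and 24. Take Week 1 as the within-patient PK reference. In the lightest weight band, Table 7 schedules only end-of-infusion and 168 h samples for Week 1, so those two concentrations are the practical reference there. SAP 15.5.4 also computes single-dose CL from AUC0-inf and multiple-dose CL from AUC0-168h; footnote this where Week 1 CL is compared with later weeks.
2. **Supporting display.** Give a simple listing or summary of exposure at Weeks 4, 12 and 24 by ADA status in the same week's pre-infusion sample, shown by dose and labelled descriptive. Do not split further by titer and NAb.
3. **Baseline ADA.** Keep it as a patient descriptor.
4. **Index.** Add these outputs to SAP 19.2.

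No new sampling is needed; the cost is a few extra outputs. The limits should be stated with them: six patients support no inference, and the by-status summary may have no ADA-negative group if most patients seroconvert. The overlay remains readable in that case.
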